## **MILESTONES**

### **FIRST DATA EXTRACTION:**

The first data extraction is the date from which the variables used for the analysis as per protocol start to be extracted. The planned first data extraction is 30 November 2019 in order to obtain early data especially for newborns and infants.

### **LAST DATA EXTRACTION:**

The last data extraction is the date from which the minimum set of data required to perform the statistical analyses leading to the results for the primary objective(s) is completely available. The planned last data extraction date is January 2025 for all age groups.

**4. AMENDMENTS AND UPDATES**

see table below

Amendment/ Update Number	Date	Section of Study Protoco l	Amendment or Update	Reason
1	June 2023	5	Milestones amended	Protocol MO40685 has been amended to extend safety and effectiveness data collection to the end of the calendar year 2024 as per EU RMP v.4.7. In addition, the study objectives have been updated to include severity as a stratification factor for non-inhibitor patients. This change will allow to report the safety of emicizumab in patients with moderate Hemophilia A without FVIII inhibitors.

## 5. MILESTONES

Milestone	Planned Date
Registration of protocol in the EU PAS register	27 November 2019
First Data Extraction	November 2019
Last Data Extraction	January 2025
Study progress report	NA
Interim report	30 Sep 2020-30 Sep 2024
Final report of study results (CSR)	30 Sep 2025
Registration of the results in the EU PAS register	30 October 2025
Publication submission	30 March 2026

## 6. RATIONALE AND BACKGROUND

Hemophilia A is an X-linked recessive bleeding disorder characterized by deficiency or absence of blood coagulation factor VIII (FVIII), which leads to a lifelong bleeding tendency. It is estimated that hemophilia occurs in approximately 1:5000 newborn males. Approximately 65% of people with hemophilia A have moderate or severe forms characterized by FVIII activity levels 1%–5% or <1%, respectively, leading to frequent spontaneous bleeding events with complications, such as arthropathy, local functional deficits, hemorrhagic shock, neurocognitive defects, and death. For patients with hemophilia A who have a severe bleed phenotype (including patients with moderate HA) current global practice guidelines ([Srivastava et al. 2020](#)) recommend that such patients should be on prophylaxis sufficient to prevent bleeds at all times.

Primary prophylaxis with FVIII replacement therapy, consisting of intravenous infusion of FVIII 2–4 times each week starting before or after the first bleed, has proven to minimize bleeding events and complications and has become standard-of-care among pediatric patients. Although effective when optimally administered, prophylaxis with intravenous infusion can be accompanied by significant burden of treatment and can impact on the quality of life of both patients and their caregivers. Although patients on FVIII prophylaxis experience low numbers of bleeds, magnetic resonance imaging scans demonstrate progressive arthropathy in up to two-thirds of patients who receive a primary prophylaxis regimen, likely due to challenging adherence and subclinical bleeds associated with low FVIII trough levels ([Ljung and Gretenkort Andersson 2015](#)).

The development of neutralizing antibodies (inhibitors) against FVIII occurs in up to 30% of patients after exposure to therapeutic FVIII concentrates and represents the most common complication of these therapies. Permanent eradication of inhibitors can be achieved in 60%–80% of patients by immune tolerance induction using intensive FVIII administration ([Santagostino et al. 2009](#); [Hay and DiMichele 2012](#)). In patients with high-titer inhibitors following re-challenge with FVIII, use of bypassing agents (BPAs) is required for the treatment and/or control of bleeding events. Unfortunately, the hemostatic effect of bypassing agents is suboptimal, and these agents are associated with higher rate of adverse events (AEs) and treatment burden ([Konkle et al. 2007](#); [Antunes et al. 2014](#)) compared with those of FVIII concentrates in patients without inhibitors ([Manco-Johnson et al. 2013](#)), in both children and adults.

Emicizumab (also known as Hemlibra®) is a humanized monoclonal modified immunoglobulin G4 antibody with a bispecific antibody structure. Given that emicizumab has no structural relationship to FVIII, its efficacy is not affected by the presence of FVIII inhibitors and is not expected to induce or enhance the development of inhibitors to FVIII or to other coagulation factors. Emicizumab clinical development program included the following studies enrolling children or adolescents: Study BH29992 (HAVEN 2) in 85 patients <12 years of age and 3 adolescent patients (aged 12–18 years of age) with inhibitors, as well as inclusion of adolescent patients as part of Study BH29884 (HAVEN 1; 32 patients with inhibitor, once a week [Q1W] dosing regimen), Study BH30071 (HAVEN 3; 8 patients without inhibitors, Q1W or every 2 weeks dosing regimen), Study BO39182 (HAVEN 4; 1 patient with inhibitors and 3 patients without inhibitors, every 4 weeks dosing regimen), Study BO41423 (HAVEN6) included patients with mild or moderate hemophilia A without inhibitors (16 patients <12 years of age and 14 adolescent patients aged 12–18 years of age), in addition, Study MO41787 (HAVEN7) recruited 55 patients from birth to ≤ 12 months of age with severe hemophilia A without FVIII inhibitors. At the time of developing this protocol, emicizumab is approved in approximately 114 countries worldwide in patients with hemophilia A with FVIII inhibitors and is approved in approximately 102 countries worldwide for the expanded indication to include patients with hemophilia A without FVIII inhibitors, including approval in the US, Japan, and the EU. In European Union, emicizumab was approved for routine prophylaxis in adult and pediatric patients with severe hemophilia A (congenital factor VIII deficiency) without inhibitor on 11 March 2019. At the time of protocol amendment, emicizumab was also approved for routine prophylaxis in patients with moderate hemophilia A (congenital factor VIII deficiency) without inhibitor with severe bleeding phenotype (European Commission Decision received on 23 January 2023). This approval was based on study BO41423 (HAVEN 6; including 51 patients with moderate disease, receiving emicizumab loading dose 3 mg/kg SC Q1W for 4 weeks followed by a maintenance dose of either 1.5 mg/kg SC QW, 3 mg/kg SC Q2W or 6 mg/kg SC Q4W based on patient preference) ([Négrier et al. 2023](#)).

While the results observed in the clinical trials supporting the benefit-risk assessment at the time of the marketing authorization application are compelling and demonstrate a favorable benefit-risk profile, experience with emicizumab in the pediatric population has been primarily based on pediatric patients with inhibitors. The post-approval evaluation of the drug's outcomes and utilization is vital to assessing whether the efficacy and safety profile observed in clinical trials match the real-world experience in all age groups. To address this, data collected by the Pediatric Network on haemophilia management (PedNet) Registry (ClinicalTrials.gov Identifier: NCT02979119) is extracted annually and analyzed according to the current protocol, and Annual Reports are generated.

## **7. RESEARCH QUESTION AND OBJECTIVES**

### **7.1 RESEARCH QUESTION**

The main research question for this study is the safety of emicizumab use in children with hemophilia A during routine clinical care. The primary safety events of interest are thromboembolic events (TEs), thrombotic microangiopathy (TMA), and anaphylaxis. However, all safety events collected in the PedNet Registry are reported. In addition to safety, effectiveness of emicizumab is evaluated by the annual bleeding rate (ABR), as reported to PedNet.

### **7.2 OBJECTIVES**

The primary objective for this study is as follows:

- To evaluate the overall safety and tolerability of emicizumab administration, in all patients and in subgroups determined by age and status of inhibitor as well as by severity for patients without inhibitors

Primary safety endpoints:

- Frequency and incidence of TEs, TMA, anaphylaxis

The secondary objectives for this study are as follows:

- To evaluate frequency and incidence of any adverse events reported to the PedNet Registry in patients treated with emicizumab, overall and in subgroups determined by age and status of inhibitor as well as by severity for patients without inhibitors

Secondary safety endpoints:

- Any AEs reported to PedNet Registry

- To describe the bleeding profile of patients treated with emicizumab, overall and in subgroups determined by age and inhibitor status

Effectiveness endpoints:

- ABR for treated\* bleeds and percentage of patients with zero treated bleeds
- ABR for joint bleeds and major bleeds
- Bleed count for soft tissue bleeds and minor bleeds

\*As per PedNet data collection, all bleeds reported are treated bleeds

## **8. RESEARCH METHODS**

### **8.1 STUDY DESIGN**

This is a non-interventional (NI) secondary data use Post-Authorization Safety Study (PASS) relying on data collected as part of the PedNet Registry. PedNet Registry will extract data (e.g., all variables) indicated in this protocol, perform the statistical analysis and provide results to the Marketing Authorization Holder (MAH) as an aggregated report. Based on this, the MAH will generate an annual PASS report and submit it to the Pharmacovigilance Risk Assessment Committee (PRAC) and/or include the annual report in the periodical benefit risk evaluation report (PBRER) depending on the time of availability of the reports.

PedNet is a multicenter, observational research database that includes patients with FVIII/IX levels < 25 IU/dL born after 1 January 2000 and treated in one of the participating Hemophilia Treatment Centers (HTCs). At the time of protocol amendment, 32 centers from 19 countries are participating in the Registry. The goal of the Registry is to include full cohorts of all consecutive patients diagnosed and treated in each center of which information on treatment and outcomes (e.g., inhibitor development, bleeds) is collected from the time of hemophilia diagnosis or time of first treatment. To prevent selection bias, patients referred to a center after development of inhibitors are not included in the database.

Data included in the Registry is collected using electronic case report forms (eCRFs). Baseline data that pertains to mode of delivery, neonatal events, diagnostic symptoms, FVIII/IX gene mutation, and family history of hemophilia and inhibitors is collected. All centers collect detailed data on treatment and outcomes (including inhibitor development and bleeds) of patients with hemophilia during the first 50 days of exposure to coagulation factor concentrate products. Following this, the centers continue to collect information at least annually until the patient reaches the age of 18. Additional information are collected regarding surgeries, hospitalizations, and AEs.

A similar level of detail is collected for patients treated with emicizumab prophylaxis. When patients treated with emicizumab receive coagulation factor concentrate products, the type of the products is recorded. It is therefore possible to evaluate the relationship between the use of FVIII/BPAs and development of TE/TMA events for patients treated with emicizumab prophylaxis.

PedNet emicizumab specific report includes patients who are treated with emicizumab. The following data includes in the reports: number of patients treated with emicizumab, duration of emicizumab exposure, number of TE, TMA, anaphylaxis, and any other AEs,

ABR for treated bleeds, percentage of zero bleeds, ABR for joint bleeds, ABR for soft tissue bleeds, ABR for major or minor bleeds, number of patients which have used bypassing aPCC agents when treated with emicizumab, number of patients which have used FVIII products when treated with emicizumab, the number of patients used rFVII when treated with emicizumab and detailed data for patients who have developed TE, TMA or and anaphylaxis. Based on the PedNet annual report, the MAH produces the PASS report annually with the following information grouped by age and status of inhibitor as well as by severity for patients without inhibitors and/or include the results in the annual PBRRER depending on the time of availability of PedNet reports:

- Number of patients exposed to emicizumab (directly from PedNet report)
- Number of patients exposed to emicizumab who experienced TE, TMA, and anaphylaxis (calculated from PedNet report)
- Proportion and incidence of each AE of TE, TMA, and anaphylaxis among patients receiving emicizumab (calculated based on information from PedNet report)
- Number of patients exposed to emicizumab and each of the following drugs: aPCC, rFVIIa, FVIII (directly from PedNet report)
- Number of patients exposed to emicizumab and each of the following drugs: aPCC, rFVIIa, FVIII, who experienced TE, TMA, and anaphylaxis (calculated from PedNet report)
- Proportion of TE and of TMA among patients exposed to emicizumab and each of the following drugs: aPCC, rFVIIa, and FVIII (calculated based on information from PedNet report)
- Number of any other AE and number of patients with any other AE (including inhibitor development, unexpected poor efficacy, local subcutaneous reactions) reported to PedNet Registry (directly from PedNet report)
- ABR for treated bleeds, percentage of zero bleeds, ABR for joint bleeds and ABR for major bleeds (directly from PedNet report)
- Bleeds count for soft tissue bleeds and minor bleeds

PedNet performs annual data extractions in January of each year. Following each data extraction, PedNet group analyzes the data according to this protocol and provide the MAH with Annual Emicizumab-Specific Reports.

## **8.2 SETTING**

PedNet Registry is the largest registry in the world for pediatric patients with hemophilia. Currently, at the time of protocol amendment, 19 European countries plus Canada with approximately 32 treatment centers participate in the registry. The registry includes data for children and adolescents up to age 18 years, and with any disease severity (FVIII < 25 IU/dL), which provides an adequate representation of the pediatric patient population.

The following criteria describe the population eligible for this study, which is a subset of the overall population participating in the PedNet Registry.

Inclusion criteria for inclusion in the PedNet Registry:

- Diagnosis of hemophilia A
- Factor VIII activity < 25 IU/dL
- Treated in one of the participating centers

Additional inclusion for emicizumab-specific analysis:

- Received prophylactic treatment with emicizumab

Exclusion criteria for the PedNet registry:

- Referral to a participating HTC after development of inhibitors
- Informed consent for participation in the PedNet Registry not obtained

Exclusion criteria for emicizumab-specific analysis:

- Inherited or acquired bleeding disorder other than hemophilia A

### **8.3 VARIABLES**

Variables with pre-defined definitions included in PedNet Registry are captured in the PedNet eCRF. Roche does not influence any aspects of data collection. Roche only uses the aggregated level of data provided by PedNet and provide the report to PRAC and/or include the data into PBRER.

#### **8.3.1 Primary Safety Variables**

Adverse events collected in PedNet Registry are not collected according to MedDRA Classification. Most events are collected according to pre-specified lists; however, free text fields are also available for each event. For the purpose of this protocol, whenever possible they are coded by Roche according to MedDRA Preferred Term (PT) level using the most current MedDRA version. A listing of the events reported by PedNet with the corresponding MedDRA attribution assigned are provided

The primary safety variables are:

- TEs
- TMAs

- Anaphylaxis (including terms of systemic hypersensitivity, anaphylaxis, and anaphylactoid events)

These events are collected for patients who receive emicizumab prophylaxis regardless of whether patients received co-treatment with aPCC, rFVIIa, or FVIII.

### **8.3.2 Secondary Variables**

The secondary variables for this study are as follows:

- Other AEs reported to the Registry including new inhibitor development, unexpected poor efficacy (unexpected poor efficacy is included in “Other” category of AE collection in the PedNet Registry eCRF).
- Bleeding event (yes/no)
- Bleed location (joint bleed, soft tissue bleed), severity (major vs. minor\*)

\*Note PedNet protocol bleed definitions are as follows:

- Major bleed: Bleed characterized by pain, swelling, limitation of motion and failure to respond within 24 hours of treatment
- Minor bleed: Bleed characterized by minor pain, minimal swelling, minimal restriction of motion, and resolving within 24 hours of treatment
- Joint bleed: any complaint requiring treatment located in a joint
- Soft tissue bleed: any complaint requiring treatment located outside the joints
- Concomitant administration of coagulation factor concentrate products (type and dose of product FVIII product, aPCC, rFVIIa) in patients receiving emicizumab.

The baseline variables for this study are as follows (baseline is defined as the time of starting emicizumab):

- Diagnosis of hemophilia A
- Exposure to emicizumab (prophylaxis)
- Age
- FVIII Inhibitor status

## **8.4 DATA SOURCE(S)**

At the time of this protocol amendment, PedNet is a collaboration of 32 pediatric HTC in 19 countries (EU and Canada), providing an infrastructure for clinical research and

management of children with hemophilia. The PedNet Registry started in 2003 and collects real-life data from all newly diagnosed children born with hemophilia and treated at the participating centers. Data collection through the PedNet Registry is summarized in the Study Design Section 8.1.

Data is collected through well-defined web-based (eCRFs using a secure data-entry system capturing all aspects of hemophilia from birth to adolescence and adulthood. The database is hosted at the University Medical Center Utrecht in the Netherlands. Centers are visited regularly for on-site data monitoring with frequency according to their size with audit of baseline information (all data entered) and bleed and medication information (10%–50% of the data entered). Data on inhibitor results are all checked and interpreted centrally. All centers perform testing for inhibitors as advised by PedNet guidelines. All participating labs use the Nijmegen modification of the Bethesda assay with local cut off values varying between  $<0.3$  BU/ml and  $<0.6$  BU/ml.

In addition to monitoring of source data, numerous pre-specified logical checks are performed on the dataset. All inconsistencies or suspected errors are resolved by queries to the centers. All centers have obtained approval of their local ethical committee according to local regulations. Prior to inclusion into the registry signed informed consent is obtained from the parents. If required by local regulations, additional consent is obtained from patients after reaching 12 years of age included in the registry.

## **8.5 STUDY SIZE**

The sample size depends on the approval and uptake of emicizumab in the countries with centers participating in the PedNet Registry. As of January 2019, PedNet enrolled 1795 patients with hemophilia A, of which 1173 patients had severe disease, 225 patients had moderate disease and 397 had mild disease. Of the patients with severe disease, 351 patients had inhibitor diagnosed between 2000 and 2019.

Assuming a constant sample size of patients with severe disease in the registry (N=1173 with severe disease regardless of FVIII inhibitor and N=351 with inhibitor), and assuming that at least 50% of these patients receive emicizumab during the 6 years of the study, the anticipated sample size is expected to be n=587 for patients with severe disease and n=176 for patients with inhibitor at the end of this 6-year study.

No data about inhibitor status is available at this stage for patients with moderate disease. Assuming a constant sample size of patients with moderate disease in the registry (N=225 with moderate disease regardless of FVIII inhibitor), and assuming that at least 15% of these patients receive emicizumab during the 6 years of the study, the anticipated sample size is expected to be n=34 for patients with moderate disease.

The table below presents possible sample sizes with the average adoption of the drug varies between 15%–75% for severe patients and 5-25% for moderate patients during the study.

The MAH acknowledges that these estimates may change if the total number of patients enrolled in the registry changes significantly during the study time. As per last interim CSR (28-Sep-2022), a total of 266 patients enrolled since the beginning of the PedNet Registry up until the clinical cutoff date of 31 December 2021 were reported to have started treatment with emicizumab (regardless of the severity). Of these, 216 patients had updated follow-up data until 31 December 2021 and were included in the CSR (80 patients with inhibitors, 132 patients without inhibitors, and 4 patients with unknown inhibitor status).

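### The last interim report left out 50 of 266 treated patients (18.8%) for follow-up not updated to the cutoff, a condition the protocol's eligibility and analysis text does not contain

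*Protocol*

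**What the plan says.** Section 8.2 sets one additional inclusion criterion for the emicizumab analysis, "Received prophylactic treatment with emicizumab", and one exclusion specific to that analysis, "Inherited or acquired bleeding disorder other than hemophilia A". Neither concerns follow-up.

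Section 8.1 describes the registry's output in the same terms: "PedNet emicizumab specific report includes patients who are treated with emicizumab". In section 8.7.1 person-years are built from the number of patients treated and their mean exposure days. In section 8.7.2 the incidence proportion is divided by the number of patients exposed.

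Section 8.5, citing the interim report of 28 September 2022, gives "a total of 266 patients enrolled since the beginning of the PedNet Registry up until the clinical cutoff date of 31 December 2021" as having started emicizumab, whatever their severity. It continues: "Of these, 216 patients had updated follow-up data until 31 December 2021 and were included in the CSR". The included patients are broken down as "80 patients with inhibitors, 132 patients without inhibitors, and 4 patients with unknown inhibitor status".

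On updating, section 8.1 says that after the first 50 exposure days "the centers continue to collect information at least annually until the patient reaches the age of 18". The limitations in section 8.9 do not mention patients left out for lack of an update.

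**The concern.** The set that was analysed is narrower than the set the protocol defines, and the protocol reports this without reconciling the two. Being updated to the cutoff is a condition on later observation. A patient followed for two years and not updated in the third would contribute nothing, including any event recorded in those two years.

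This matters most for the primary endpoints. Thromboembolic events, thrombotic microangiopathy and anaphylaxis are rare, and a single event more or less changes the message of the report. The sponsor receives only aggregate results (sections 8.7, 8.8 and 9.1), so it cannot restore the omitted patients itself. The rule has to be in the protocol that the registry applies.

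**Working it through.** **Inputs, all from section 8.5:** 266 patients started emicizumab; 216 were included in the interim report; of these, 80 had inhibitors, 132 did not, and 4 had unknown status.

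**The protocol's own figure.** 80 + 132 + 4 = 216, so the breakdown is consistent with the stated total.

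**Patients left out.** 266 − 216 = 50, and 50/266 = 18.8%.

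**Where a follow-up condition could stand:**
- Eligibility (8.2): treatment with emicizumab; no follow-up condition.
- Report definition (8.1): treated patients; no follow-up condition.
- Person-years (8.7.1): number treated and mean exposure; no follow-up condition.
- Incidence proportion (8.7.2): patients exposed; no follow-up condition.
- Limitations (8.9): silent.
- Study size (8.5): the condition appears only here, as a description of one past report.

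**Effect on precision with no events.** The exact two-sided 95% upper limit for 0 events in n patients is 1 − 0.025^(1/n).
- n = 216: 1.69%
- n = 266: 1.38%
- n = 50, the omitted patients alone: 7.1%. Even if none of the 50 had an event, that group by itself would say little.

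**Chance that an omitted group of 50 contains at least one event:** 1 − (1 − p)^50. The documents give no risk, so p is assumed over a range.
- p = 0.5%: 22%
- p = 1%: 39%
- p = 2%: 64%

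**Size of any bias.** Let the risk in the 50 be k times the risk in the 216. The proportion from the 216, relative to that in all 266, is 266/(216 + 50k). The values of k are assumptions.
- k = 1: 266/266 = 100%, no bias
- k = 2: 266/316 = 84%
- k = 3: 266/366 = 73%
- k = 5: 266/466 = 57%

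**Do the planned methods need the filter?** No. Number treated times mean exposure is total exposure, however unevenly it is spread, provided both figures come from the same patients. The negative-binomial model for bleeding rates is offset by each patient's duration of follow-up. The incidence proportion is different: it ignores follow-up time, so patients with short follow-up pull it down.

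**The case against.** The strongest reply is that the protocol prescribes no such filter. Section 8.5 describes one past interim report, and the operative text already covers all treated patients. That is correct. The conflict is between reported practice and written rules, not between two rules.

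A reader might go further in four ways that the documents do not support:

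- **That all reports use the filter, or that it will recur in the final one.** One interim report is evidence for one report. Sections 8.1 and 8.6 provide for updates at regular visits and at least annually, so a patient who is behind at one cutoff may be current at the next. The synopsis describes the last extraction as the point when the minimum data for the primary objective are completely available. Still, no later report would pick up a gap left in the final one, and the protocol does not say which set that report uses.
- **That the 50 are patients who died, left, stopped treatment or turned 18.** No reason is given. Ordinary data-entry lag fits equally well and need not be related to risk.
- **That events have been lost.** This is not shown. Section 10 requires investigators to notify adverse events and provides for quarterly reports, which is another route for recording events. It does not establish that events in the 50 reached the interim report. Some of the 50 may also have no recorded follow-up after starting, so the person-time forgone is unknown.
- **That Table 1 must shrink by 216/266, for example from 587 to about 477.** This applies a mid-study share, taken over all severities, to the final numbers in each group. Table 1 is a range over assumed adoption with no hypothesis test behind it, and section 8.5 says the estimates may change.

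What stands after this is that a condition absent from the protocol was applied to almost a fifth of treated patients, and that its future use is left open.

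**Conclusion.** The point holds in a limited form. In the one report the protocol describes, 50 of 266 treated patients (18.8%) were left out under a condition that sections 8.1, 8.2 and 8.7 do not contain. The protocol does not say why, or whether the final report will do the same.

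If the filter is used again, the certain cost is whatever recorded exposure the omitted patients have. With no events, the difference between the two denominators is an upper limit of 1.69% against 1.38%. Bias is possible but depends on the omitted patients having a different risk, and its direction is unknown. The percentages for k above 1 illustrate assumed values and are not estimates. The matter should be settled before the final analysis, because it decides the denominator, the person-time and possibly the event count for the primary endpoints.

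**What to change.** - State in sections 8.2 and 8.7 that all patients who received prophylactic emicizumab are analysed, with events and person-time counted to the last registry update, or to end of exposure if earlier. The number of patients and the mean exposure days supplied by the registry should refer to this same set.
- Report the number of patients not updated to the cutoff, with their last status and known events.
- Present the updated-to-cutoff subset as a sensitivity analysis.
- Show the incidence proportion for both sets.

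The cost is one rule and a small addition to the registry's annual report, using data the registry already holds. The downside is less uniform follow-up. The incidence rate and the bleeding-rate offset handle that. The incidence proportion does not, since truncated follow-up can lower it, which is why it should be shown both ways.
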